### **Phase I. Open trial and RCT**

**Study overview.** In this treatment development grant, 70 adolescents in Probation will be recruited to participate in the study. The first 10 will participate in an iterative development open trial. Then 60 youth will be randomized to: 1) the screening/brief intervention safety planning intervention, or 2) standard practice.

**Open Trial Design.** A total of 10 youth will be recruited for open trial in order to: a) test the protocol's applicability in Probation, and b) train the mental health counselors in the protocol. We have used this 2 phase approach extensively in prior studies. The open trial will occur in months 5 - 8 after counselor training. The protocol and procedures will be modified as necessary after the first 5 participants and then again after 10 pilots have been run through the protocol and prior to conducting the pilot RCT

[figure not shown]
**Overview of RCT Trial Procedures.** When youth arrive for their first Probation appointment, they are asked to complete the MAYSI/NSSI assessment. Youth who flag in on the MAYSI or NSSI item on this first screen, will be referred by their PO to the mental health counselor who will approach them about participation in the study. If the parent/caregiver consents to the study, the mental health counselor will then meet with the youth, physically separate from the parent/caregiver, to describe study procedures in detail (**including the fact that only youth who are positive on the secondary screen continue in the study**) and obtain juvenile assent without parental presence (see **Human Subjects**). Consenting procedures will also include permission to access court records. All youth will then complete the complete the Self-Injurious Thoughts and Behaviors Interview 2.0 (SITBI-Short Form^91, see below), to more thoroughly assess self-injurious behavior. Families will then be referred back to their PO to complete the secondary screen. If the youth screens in, he/she is then randomized to either standard practice or the safety planning intervention.

Follow-up assessments will also be completed at 1- and 3-months post-baseline to gather data on youth outcomes related to treatment, self-harm, and recidivism. No juvenile will ever be sanctioned by the court for not agreeing or being unable to participate in the research study (see **Human Subjects/Letter of Support**).

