If a juvenile flags in and is in the experimental condition, the safety planning will occur in three stages: 1) the juvenile will meet with a trained mental health counselor to create the safety plan; 2) the juvenile and counselor will meet with the PO and caregiver to share the safety plan and discuss strategies and challenges to implementing the safety plan; and 3) the PO will then contact the current mental health provider or appropriate community mental health clinic to facilitate an outpatient appointment, if the youth is not at immediate risk. In cases where substance use is an issue, the JJS staff member will ask permission of the youth to relay this to the community mental health clinic or current provider.

The Safety Plan intervention, *which consists of the one module from Co-I [name]'s COPES program described above*, incorporate the SITBI responses, which covers both suicidal and nonsuicidal ideation and behavior, to ensure all areas are covered in the Safety Planning process. For example, the SITBI will identify suicide means youth have thought about using. Youth make a list of dangerous items to remove from their surroundings (e.g., alcohol, knives, razors, medications) in order to reduce access to means, identify their warning signs and vulnerabilities that indicate they may become unsafe, generate helpful coping strategies, and identify people that can help them manage negative feelings.

*The safety plan intervention concludes with a section emphasizing completing referrals for outpatient care for those youth. Youth will also complete the 8-item Motivation for Youth's Treatment Scale (MYTS) to facilitate discussion between the counselor and the youth about the youth's current motivation for treatment. At the same time, the caregiver will complete the Barriers to Treatment Participation Scale (BTPS) that will inform the mental health counselor about potential barriers (identified as "often a problem" or "always a problem") and promote discussion during the safety planning with the youth and caregiver about those potentials barriers and generate ideas on how to overcome them.*

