**Brief Intervention Follow-up Phone Call.** One week after the in-person safety planning, the mental health counselor will contact the teen's parent/caregiver to review elements of the safety plan and problem-solve barriers to using the safety plan and engaging in treatment. If the family has not made contact with a treatment provider, the mental health counselor will further assist the family in setting up an appointment. Co-I

[name]'s research with recently incarcerated and suicidal individuals has shown that telephone follow-up intervention is feasible, acceptable, and powerful in building trust and reducing risk among these populations.

**Baseline and Follow-up Assessment.** In order to pilot test a procedure with the greatest potential to be implemented in a large effectiveness trial in the future, we collect all baseline data from information collected routinely and recorded in court records, with the exception of administering the SITBI. Therefore, potential participants will not be paid for the completion of the baseline measures. The consent form will specify that, as part of participating in the study, the MPIs will be allowed to use the baseline data from the RIFC chart.

The follow-up assessment battery was also designed to reduce participant burden and will be scheduled at 1 and 3 months post-intervention. The 3-month follow-up period will allow us to assess a high-risk period for self-injury as well as the typical period of time that adolescents remain in outpatient psychotherapy. Follow up interviews will be conducted in-person and last approximately 1 hour. Juveniles and a caregiver will each be compensated \$30 for the time to complete the 1 and 3-month assessment.

**Protection against Attrition.** We do not anticipate a great deal of attrition at the 1 and 3-month follow-up assessment, based on our prior success in following participants in our other treatment studies. Nonetheless, after the baseline assessment, participants will be educated on the importance of completing the follow-up assessments; provided the date and time of the follow-up appointments, and provided a study contact number to call if contact information changes. Detailed tracking information will be recorded. Our retention strategies will include phone, texting, email, and postal mail contact (e.g., personalized holiday, thank you, and birthday cards). In addition, names of two friends or family members will be requested in the event that research staff is

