#### **Youth level outcomes**

Feasibility of a future larger trial, will be defined as the percent of at-risk youth who enroll in the research project. Feasibility of conducting safety planning in Probation will be assessed by the percentage who receive the brief intervention, including linkage to treatment and the follow-up phone call, in total and in part.

Acceptability will be assessed by post-intervention ratings on the Client Satisfaction Questionnaire [CSQ-8;120], a well-established 8-item self-report instrument on a 4-point scale used to assess patients' satisfaction with psychiatric treatment. A score above 24 is the benchmark based on previous research. An "exit interview" will also be conducted at the one month follow-up about the intervention protocol that they received.

The Self-Injurious Thoughts and Behaviors Interview 2.0 (SITBI 2.0) Short Form^91 is a structured interview designed to assess the presence, frequency, and characteristics of a broad array of self-injurious thoughts and behaviors. The SITBI has good reliability and validity. The SITBI will be completed at baseline and 1 and 3-month follow-up to assess suicidal ideation, attempts, and NSSI. Suicidal events will be operationalized as a composite score of suicide attempts and emergency interventions for acute suicidality assessed by the CASA (see below). Recidivism (collateral data from RIFC database) including new arrests, description of related charges (e.g., substance-related, property) and time detained/incarcerated (all tracked by the RIFC database) will be available.

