**Primary Aim.** Our primary aim is to examine feasibility and acceptability of the safety planning intervention to inform next-step study design. **Feasibility** of a larger future trial will be evaluated based on: a) enrollment rates for the research project (target = 70%), and feasibility of the intervention, b) the percentage of participants who complete the entire intervention protocol (target = 70%). We will also determine the appropriateness of our assessment battery for a larger, future trial, by examining whether the range of responses to instruments indicate sufficient variability and change over time. **Acceptability** will be demonstrated by study withdrawal (< 20%) and > 80% of the responses on a consumer satisfaction scale rated as highly satisfactory. We will use logistic regression to model binary outcomes of enrollment, completion of the protocol, and withdrawal as a function of treatment assignment. We will use ordinal logistic regression for the satisfaction scale analysis.

With respect to youth level clinical outcomes, the goal is to obtain a reasonably precise estimate of the standard deviation for the outcome variables, and pre-post correlations of outcome variables, which are essential statistics for powering a definitive trial. Following Leon et al (2011) and Kraemer et al (2006), our goal is not to obtain a preliminary estimate of the treatment effect size, but as per Teare and colleagues (2014), the size of the pilot we propose is sufficient to obtain sufficiently precise estimates of key variance and covariance parameters necessary to design a definitive trial. Our approach will be to conduct an analysis consistent with the testing of the hypothesis that JJS youth enrolled in the experimental condition have less self-injurious ideation and behavior at 1 and 3 month follow-up relative to youth enrolled in standard practice. We will also examine mechanisms including treatment attendance, safety skill acquisition, motivation for

treatment, and treatment barrier reduction. The main outcomes are suicidal ideation and suicide attempts/NSSI on the SITBI.

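### Enrollment cannot be regressed on treatment assignment, because it comes before randomization; the same model for completion is valid only if completion means the study assessments

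*Combined protocol and SAP*

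**What the plan says.** The Primary Aim paragraph of the Phase I Data Analysis Plan sets two feasibility criteria. One is an enrollment rate with a target of 70%. The other is "the percentage of participants who complete the entire intervention protocol (target = 70"%). Acceptability is judged by withdrawal below 20% and by satisfaction ratings. The plan then names the model: "We will use logistic regression to model binary outcomes of enrollment, completion of the protocol, and withdrawal as a function of treatment assignment". Satisfaction gets a separate ordinal logistic regression.

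The Youth level outcomes section defines the two feasibility measures. Feasibility of a future trial "will be defined as the percent of at-risk youth who enroll in the research project". Feasibility of the intervention is "the percentage who receive the brief intervention, including linkage to treatment and the follow-up phone call", counted both in total and in part.

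The Overview of RCT Trial Procedures gives the order of events. A positive first screen leads to an approach about the study. Next: "If the parent/caregiver consents to the study, the mental health counselor will then meet with the youth", to explain the study and obtain assent. The SITBI and the secondary screen follow. Only then: "If the youth screens in, he/she is then randomized to either standard practice or the safety planning intervention".

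On who receives the intervention, the Safety Planning section says: "If a juvenile flags in and is in the experimental condition, the safety planning will occur in three stages". The phone-call section adds: "One week after the in-person safety planning, the mental health counselor will contact" the family. Under Current standard practice, control youth receive a referral and a resource packet, but no safety plan and no call.

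**The concern.** A regression on treatment assignment needs an outcome that can differ among people who have an assignment. Enrollment is settled before any assignment exists. Completion of the intervention, if that is what the second outcome means, is possible in one arm only. Of the three outcomes named, only withdrawal is plainly suited to the model.

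Feasibility and acceptability together form the primary aim, and this sentence names the only model for the feasibility outcomes. The Power paragraph says that high feasibility and acceptability would support a larger trial. An analyst following the plan would find that one of the three regressions cannot be run, and would have to decide after the fact what the second one means. Even where a by-arm odds ratio exists, it does not show whether a 70% target was met.

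**Working it through.** The documents give no sample size, power or precision for these models, so there is no figure to reproduce. The check is whether each model can be estimated.

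**Inputs.** 60 youth randomized (Study overview); the order of events (Overview of RCT Trial Procedures); 70% targets for enrollment and for intervention completion (Primary Aim). The allocation ratio is not stated, so 30 per arm is assumed. The Power paragraph puts 70 in the RCT, but the structural results are the same for either total.

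**Model.** logit P(Y = 1) = b0 + b1 × arm.

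**Enrollment.** There are two possible meanings.

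- Enrolled means consented: youth who decline have no value for arm, and neither do consented youth who are negative on the secondary screen. They drop out of the model, leaving the 60 randomized, all with Y = 1.
- Enrolled means randomized: again Y = 1 for all 60 youth with an arm.

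Either way the likelihood rises without limit as b0 increases, and b1 is not identified. A Newton fit to 60 outcomes all equal to 1 stops with a singular matrix.

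**Completion, read as the intervention protocol.** Suppose 21 of 30 complete in the safety planning arm. Control completion is 0 of 30 by design.

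- b1 = ln(21/9) − ln(0/30) = 0.85 − (−∞), which is not finite.
- An iterative fit confirms it: the log odds ratio is 7.4 after 5 iterations, 12.4 after 10, 22.4 after 20 and 27.4 after 25, while its standard error goes from 3.0 to 36, 5,337 and 65,019. These are stopping points of a fit that does not converge, not estimates.
- If the denominator is all participants, 21 completers give 21/60 = 35%, and the largest possible value is 30/60 = 50%. The 70% target would be out of reach by construction.

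**Completion, read as the study assessments.** The outcome is defined in both arms and the model can be fitted, but it does not address the 70% intervention target.

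**Withdrawal.** This can be fitted. For an illustrative 8/30 in standard practice and 4/30 in safety planning, the log odds ratio is ln[(4/26)/(8/22)] = −0.86, with SE = √(1/4 + 1/26 + 1/8 + 1/22) = 0.68.

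**Single-proportion alternative.** The exact (Clopper-Pearson) 95% limits for x of n are the 2.5% point of Beta(x, n − x + 1) and the 97.5% point of Beta(x + 1, n − x).

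| Measure | Count | Proportion | Exact 95% CI |
|---|---|---|---|
| Intervention completion, 30 in arm assumed | 21/30 | 70% | 50.6% to 85.3% |
| Enrollment near the 70% target (60/0.7 = 85.7, taken as 86) | 60/86 | 69.8% | 58.9% to 79.2% |
| Enrollment at 60% acceptance (60/0.6 = 100) | 60/100 | 60% | 49.7% to 69.7% |

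The enrollment rows assume that recruitment stops at 60 and that the denominator is youth positive for current risk. The 60% is the acceptance rate in Estimated Sample Size and Retention Rates. If at-risk means positive on the first screen, which is when families are approached, these denominators do not apply.

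**The case against.** For enrollment there is no good answer. The flow figure is missing from the available text, but the written order is explicit, and no passage names another predictor for enrollment or gives non-enrollees an arm.

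For completion the objection has force. The model sentence speaks of the protocol, not the intervention protocol. Elsewhere the plan uses the word for the follow-up assessments, and it tests differential attrition by condition. A by-arm comparison of assessment completion would be coherent. Against that, the nearest antecedent in the same paragraph is the intervention protocol. This part is therefore an undefined term, not a demonstrated error. Intervention receipt is also measured in part, and because standard practice includes referral, linkage alone can be compared between arms. A penalized fit would give a finite number for the whole intervention, but it would only reflect that controls were not offered it.

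A reader might infer that enrollment cannot be analyzed at all, or that the primary aim fails. The documents do not support this: enrollment is judged as a rate against 70%, and that rate remains computable. A reader might also take the 60% acceptance rate as contradicting the 70% target. It does not, because the plan presents 60% as a conservative planning figure. That the interval for 60/100 excludes 70% is a property of that illustration, not a prediction.

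Finally, the targets are point criteria, and the plan states no precision for them. Confidence intervals are good practice, but they are not needed to repair the sentence.

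**Conclusion.** The enrollment regression is wrong as written and cannot be fitted under either meaning of enrolled. This does not depend on the allocation ratio or the number randomized. The completion regression is conditional: degenerate if it refers to the intervention protocol, valid but off target if it refers to study assessments, and the plan does not say which. The 50% ceiling on completion assumes 1:1 allocation and both arms in the denominator. Withdrawal by arm is correctly specified.

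The consequence is limited. The percentages can still be compared with their targets, no sample size or clinical-outcome analysis rests on this sentence, and the failure would be visible instead of biasing a result silently. It should still be corrected, because it is the prespecified model for the feasibility part of the primary aim.

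**What to change.** 1. Delete enrollment from the regression sentence. Report it as one proportion of at-risk youth with an exact 95% confidence interval beside the 70% target. State which screen defines at-risk, and whether enrolled means consented or randomized.
2. Report intervention completion as one proportion among youth randomized to safety planning, with an exact 95% interval beside its 70% target. Linkage may be compared by arm as a separate outcome.
3. Define what completion of the protocol means. Keep the by-arm logistic regression for withdrawal and, if it was intended, for completion of the study assessments, named as such.
4. Leave the point targets as the criteria; the intervals show how precisely they are measured.

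The cost is a change of SAP wording, plus counts of youth screened, consented and randomized. The analyses are simpler than those now planned, and trial conduct does not change.

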We will use generalized linear mixed models to test hypotheses that participants randomized to the safety plan condition will have significantly improved outcomes compared with those who receive standard practice. This approach accommodates varying numbers of observations across individuals (allowing the inclusion of all randomized participants) while controlling for within-subject correlation. Scores from continuous measures are the dependent variables and treatment condition is the primary independent variable. Analyses will also be conducted co-varying baseline SITBI scores. These hypotheses will be evaluated by regressing the outcome variables as observed on the 1 and 3-month follow-ups on treatment condition, and a time by treatment condition interaction in a general linear mixed effect modeling framework. Main inferences will be based on post-hoc omnibus tests of treatment group effects pooled over time points, and secondary inferences will be drawn from the time-specific outcomes.

The current study also seeks to illuminate factors that may better guide treatment decision making by identifying those who are most likely to benefit from the proposed interventions. Specifically, in exploratory analyses, we will examine sex, race, and ethnicity to address the barrier of racial disparities.

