**Power:** We will recruit 70 participants in the RCT which should be sufficient to make judgments regarding feasibility and acceptability. We do not have pilot data available for calculating effect sizes to present here because R34 applications do not require pilot data but are used to collect pilot data regarding feasibility and acceptability. Two-way comparisons across treatment groups result in 80% power to detect effect sizes amounting to standardized mean differences (Cohen's d) of 1.0 or higher as statistically significant under a two-sample t-test analytic framework. With repeated measures for outcomes, under assumptions of reasonable reliability for the outcomes ( $r = .8$ ) and high autocorrelation for repeated measures ( $r = .64$ ), we will be able to detect smaller differences ( $d = .62$ ) in pairwise comparisons (where  $.62 = (16*(1-.8^2)/15)^{0.5}$ , following Lehr [137]). A medium ES when power is set at .8, is typically considered a clinically relevant finding. Thus, if high levels of feasibility and acceptability are found, this would suggest that the protocol should be tested in a larger trial. For power of .8 and a clinically relevant ES, i.e., a medium ES ( $d = .5$ ), a sample of 64 per group would be required in a future R01.

**Aim 2: Service level mechanisms** will be examined as potential mediators of intervention effects. Success of treatment linkage, including barriers to outpatient treatment, and the equity of intervention fidelity and treatment linkage across sex, race, and ethnicity will be compared following the analytic approach summarized in Aim 1.

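### The plan says a treatment-effect estimate is not the goal for clinical outcomes, yet makes significance tests of benefit the main inference for them

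*Combined protocol and SAP*

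**What the plan says.** The Primary Aim paragraph of the Phase I Data Analysis Plan opens with "Our primary aim is to examine feasibility and acceptability of the safety planning intervention to inform next-step study design". For youth clinical outcomes it then says that what is wanted is standard deviations and pre-post correlations for designing a definitive trial, and that "our goal is not to obtain a preliminary estimate of the treatment effect size". A few lines later it adds a bridging sentence, "Our approach will be to conduct an analysis consistent with the testing of the hypothesis", referring to less self-injury in the experimental arm. It names suicidal ideation and suicide attempts/NSSI as the main outcomes.

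The paragraph on generalized linear mixed models goes further. Its purpose is to "test hypotheses that participants randomized to the safety plan condition will have significantly improved outcomes" relative to standard practice, and "Main inferences will be based on post-hoc omnibus tests of treatment group effects pooled over time points", with time-specific results secondary. The word exploratory appears in this section only for the analyses by sex, race and ethnicity.

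The Power paragraph calls d = .5 clinically relevant and says that detecting it would take 64 per group in a future trial. It links progression to other criteria: "if high levels of feasibility and acceptability are found, this would suggest that the protocol should be tested in a larger trial". It gives no power for the pooled test. The Data Analysis Plan contains no multiplicity rule.

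**The concern.** A test of benefit is a stronger claim about the treatment effect than a preliminary estimate of it. A plan that disclaims the estimate but bases its main inference on the test leaves the team without a clear rule for what the clinical results may be used to say.

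What is at stake is reporting. If the mixed-model paragraph is followed literally, the lead statement on youth self-injury will be that an effect was, or was not, significant. In a trial of this size, failure to reach significance says little about whether a worthwhile effect exists, but readers may take it as evidence of no effect. An isolated significant result among several outcomes could be over-read in the other direction.

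**Working it through.** **Inputs from the documents**
- Randomized: 60 in two arms (Study overview).
- Expected at 3 months: 48, from 80% follow-up (Estimated Sample Size and Retention Rates).
- Autocorrelation of repeated measures ρ = .64, and clinically relevant effect d = .5 (Power).
- Unadjusted analyses primary, adjusted ones secondary (opening of the Data Analysis Plan). ANCOVA on baseline is also planned there, without a clear rank.

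**Assumptions, not in the documents**
- Two-sided .05. This fits the constant 16 in the plan's Lehr formula.
- 1:1 allocation, so 30 per arm randomized and 24 per arm at 3 months.
- The same effect at both visits, and an approximately normal outcome.
- Baseline to follow-up correlation r, and d = .3 as a smaller effect. Both are illustrations.

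**The plan's own figures**
- Repeated measures: √(16 × .36 / 15) = √.384 = .62. Reproduced.
- Single comparison: √(16 / 15) = 1.03, close to the stated 1.0. Exact t power at d = 1.0 with 15 per group is 75.3%.
- Future trial: 16 / .5² = 64 per group, with exact power 80.1%. Reproduced.

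The first two use 15 per group rather than 30. That is a separate matter, and the calculations below use the planned arm sizes.

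**Power of the pooled test, unadjusted**

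The mean of two visits has variance factor f = (1 + ρ)/2 = (1 + .64)/2 = .82. The noncentrality is (d/√f) × √(n/2), with 2n − 2 degrees of freedom.
- d = .5, n = 30: (.5/.906) × √15 = 2.14, power 55.7%.
- d = .5, n = 24: (.5/.906) × √12 = 1.91, power 46.5%.
- d = .3, n = 30: noncentrality 1.28, power 24.3%.
- d = .3, n = 24: noncentrality 1.15, power 20.2%.

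**Power at d = .5 with baseline as covariate**, f = .82 − r²

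| r | f | 30 per arm | 24 per arm |
|---|---|---|---|
| .3 | .73 | 60.6% | 51.0% |
| .5 | .57 | 71.3% | 61.3% |
| .64 | .41 | 84.4% | 75.4% |

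**Precision of the unadjusted pooled contrast**

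The 95% half-width is t × √(2f/n).
- n = 30: 2.002 × √(1.64/30) = 0.47 SD.
- n = 24: 2.013 × √(1.64/24) = 0.53 SD.

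With 30 per arm, a non-significant estimate of 0.25 SD in favour of the intervention would have an interval from 0.25 − 0.47 = −0.22 to 0.25 + 0.47 = 0.72. That contains both zero and the plan's d = .5.

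**Multiplicity**

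The main outcomes count as two (ideation; attempts/NSSI) or three (attempts and NSSI separated). If the tests are independent, the chance of at least one false positive is 1 − .95² = 9.75% or 1 − .95³ = 14.3%. Positive correlation between outcomes taken from one interview would lower both figures.

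**The case against.** The strongest reply is that the pilot does not depend on these tests. Its primary aim and numeric targets concern feasibility and acceptability, and the Power paragraph rests the case for a larger trial on the same ground. It also says openly that d = .5 needs 64 per group. All of this stands. A reader might infer that a chance p-value could stop or promote the intervention, but no section ties progression to significance.

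A second reply is that the bridging sentence "Our approach will be to conduct an analysis consistent with the testing of the hypothesis" can be read as rehearsing the definitive trial's model. That is a fair reading of that sentence. It does not cover the mixed-model paragraph, which drops the qualification and speaks of main inferences.

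Third, power may be better than the unadjusted figures suggest. Baseline adjustment is planned in some form, the mixed model uses 1-month data from youth lost later, and multiple imputation is foreseen, so 24 per arm is a pessimistic case. If r were as high as .64, adjusted power would be 84% or 75%. With the plan's own factor of .36 it would be 89% or 81%. That factor, however, does not describe an unadjusted mean of two visits, and the plan ranks unadjusted analyses first.

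Some stronger readings are tempting but not supported:
- **The main test has under 50% power.** At d = .5 with 30 per arm, 47.8% belongs to an unadjusted t-test at one visit (39.6% with 24 per arm). The pooled test falls below 50% only when unadjusted with 24 per arm, on a two-degree-of-freedom reading (46.7% or 38.4%), or for a smaller effect.
- **The omnibus test is the wrong, directionless test.** This assumes a joint test of treatment and interaction. Pooling over time points, set against time-specific results, more naturally means an averaged effect. The label post-hoc can mean post-estimation, since the test is written into the plan.
- **An uninformative null or a chance finding is the most likely result.** At d = .5 the chance of a null is about 44% to 54% unadjusted, and lower with adjustment. A rejection when d = .5 is true is not a chance finding.
- **There is about a 30% chance of a false positive.** That needs seven independent tests, counting four mechanisms that the plan says only that it will examine.

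**Conclusion.** The concern holds as an inconsistency about what the pilot may conclude on clinical outcomes. One paragraph disclaims a preliminary effect estimate, and the next makes tests of benefit the main inference without marking them exploratory.

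On the stated assumptions, the unadjusted pooled test has roughly even odds of detecting d = .5 and only a one-in-four to one-in-five chance of detecting d = .3. A null would leave an interval about half an SD wide on each side. The false-positive chance across the main outcomes is at most about 10% to 14% for independent tests.

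Two limits apply. The figures suit a roughly continuous score. Attempts and NSSI may be sparse, which could lower power for them, but the documents give no rates. The Power paragraph also says "We will recruit 70 participants in the RCT" where the Study overview has 60 randomized after a 10-youth open trial. At 35 per arm the unadjusted pooled power at d = .5 would be about 62% (noncentrality (.5/.906) × √17.5 = 2.31), which does not change the conclusion.

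The point should be corrected, but it does not undermine the pilot's primary aim.

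**What to change.** In the mixed-model paragraph, remove the language about significantly improved outcomes and about main inferences from post-hoc omnibus tests. In its place, state that:
- for each main outcome, one pre-specified one-degree-of-freedom treatment contrast, averaged over 1 and 3 months, will be reported with its 95% confidence interval, and the plan will say whether that contrast is unadjusted or baseline-adjusted;
- within-arm standard deviations and correlations will be reported beside it, as the Primary Aim paragraph intends;
- these clinical analyses are exploratory, and no conclusion on efficacy will rest on statistical significance.

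This agrees with the Power paragraph, where the case for a larger trial rests on feasibility and acceptability. Design, data collection and sample size do not change. The cost is a wording change, and the team gives up a possible significant headline result.
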